# 6.4 Prior Therapies

Prior cancer treatment, including types of prior therapies will be summarized using the Safety Analysis Set.

#### 6.5 Treatment Administration

Treatment administration will be summarized for safety analysis set. Summary statistics for duration of therapy and the number of cycles per patient will be presented, as well as the number and percentage of patients who were treated at each cycle and completed each cycle.

# 6.6 Efficacy Analyses

The primary analysis of efficacy endpoints will be analyzed using the All Treated analysis set. The ORR, DCR, DOR, and PFS will be summarized per RECIST Version 1.1 (Eisenhauer 2009).

# 6.6.1 Efficacy Endpoints

# 6.6.1.1 Objective Response Rate (ORR)

ORR is defined as the proportion of patients with confirmed CR or PR according to RECIST Version 1.1. Patients who do not have at least 2 (initial response and confirmation scan) postbaseline response assessments will be counted as non-responders.

The observed ORR and the 95% confidence intervals will be provided using Clopper-Pearson methodology.

The maximum percent reduction (or minimum percent increase if there is no reduction) in the sums of diameters from baseline will be derived for each patient and will be graphically displayed (e.g., using a waterfall plot).

#### 6.6.1.2 Duration of Response (DOR)

Duration of response (DOR) according to RECIST Version 1.1 is defined as the time from first documentation of objective response (that is subsequently confirmed) per investigator to the first documentation of disease progression, or to death due to any cause, whichever comes first. Disease progression includes radiologic evidence of tumor progression and clinical progression per investigator.

Duration of response will only be calculated for the subgroup of patients achieving a confirmed CR or PR. Duration of response will be analyzed using Kaplan-Meier methodology and Kaplan-Meier plots will be provided by expansion cohorts and overall. The Study SGNLVA-002

Statistical Analysis Plan

O1-May-2024
Ladiratuzumab vedotin

Seagen, Inc. - Confidential

Page 17 of 32

median duration of response and its two-sided 95% CI using the complementary log-log transformation method (Collett 1994) will be calculated for each expansion cohort and overall.

DOR data will be censored as described below:

- Patients who do not have PD and are still on study at the time of an analysis will be censored at the date of the last disease assessment documenting absence of PD;
- Patients who have started a new antitumor treatment (with the exception of palliative radiotherapy on a non-target lesion that is not progressing) prior to documentation of PD will be censored at the date of the last disease assessment prior to start of new therapy;
- Patients who are removed from the study prior to documentation of PD will be censored at the date of the last disease assessment documenting absence of PD.
- Patients who have deaths or PD per RECIST v1.1 occurring after two or more missed visits will be censored at the last disease assessment;

#### 6.6.1.3 Disease Control Rate

Disease control rate (DCR) is defined as the proportion of patients with CR, PR, or SD per RECIST Version 1.1.

The observed DCR and the 95% confidence intervals will be provided for the All Treated analysis setusing Clopper-Pearson methodology, by expansion cohorts and overall.

# 6.6.1.4 Progression-Free Survival (PFS)

Progression-free survival (PFS) is defined as the time from start of study treatment to first documentation of disease progression (PD) based upon the disease assessment per RECIST Version 1.1 or clinical progression, or to death due to any cause, whichever comes first. For patients who are enrolled but fail to receive study treatment, the enrollment date will be used as the starting point in the calculation in PFS. Specifically,

PFS = Date of first documented PD or death - Date of first study treatment +1

The same censoring rules outlined for DOR will be applied to PFS. Patients lacking an evaluation of tumor response at baseline and/or after their first dose will have their event time censored at Day 1.

PFS will be analyzed using the Kaplan-Meier method and Kaplan-Meier plots will be provided. The median PFS and its two-sided 95% confidence intervals (CI) will be calculated using the complementary log-log transformation method (Collett 1994) by expansion cohorts and overall.

Page 18

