1.2. Triple-Negative Breast Cancer

Triple-negative breast cancer (TNBC) accounts for approximately 10%–20% of BCs. These tumors lack estrogen, progesterone, and HER2 receptors and are associated with poorer prognosis compared to other types of BC. TNBC has a high proliferative rate and a heterogeneous gene expression profile. Patients with metastatic triple-negative breast cancer (mTNBC) have a median overall survival (OS) of less than 1 year (Rodler 2010; den Brok 2017).

The lack of hormone and HER2 receptors limits treatment options in TNBC to currently available chemotherapy in both the local and metastatic settings. Considerations for treating locally-advanced or metastatic (LA/M) disease include previous chemotherapy exposure. performance status, comorbid conditions, tumor characteristics, patient preference, and quality of life concerns. Sequential single-agent systemic chemotherapies associated with minimal toxicity are preferred. Commonly used single agents include taxanes and anthracyclines. Standard clinical practice is to continue first line chemotherapy until progression. The choice of chemotherapy for mBC is not well defined. There are no published evidence-based clinical guidelines with explicit recommendations about what systemic treatment is more appropriate for these patients with advanced TNBC. In recent Phase 2 and 3 TNBC trials on first line singleagent chemotherapies, including taxanes, platinums, and anthracyclines, the ORR was approximately 29%-40% and the median progression-free survival (PFS) was 3-6 months (Helwick 2015; Isakoff 2015; Rugo 2015). Combination therapies of traditional chemotherapeutic agents (e.g., gemcitabine + carboplatin) are also used. Recent analyses show combination therapies confer little to no survival benefits and have a higher toxicity profile when compared to the sequential single-agent chemotherapy (Carlson 2011; Dear 2013).

Given the current landscape, there is an obvious and urgent need for novel therapies in the first line LA/M setting that can provide clinical and survival benefit.

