7.2. Response/Efficacy Assessments

Treatment response will be assessed by radiographic tumor evaluation every 6 weeks (±3 days) for 12 months after the first dose of LV and pembrolizumab and every 12 weeks (±7 days) thereafter and should be calculated from Cycle 1 Day 1 during treatment. Time points for radiographic examinations should be calendar based and do not depend on cycle visits. The schedule of response assessments should not be adjusted for dose delays, dose interruptions, or other reasons for changes in the timing of a patient's study activities. No additional scans or response assessments are required after the safety follow-up period, however additional scans or response assessments may be performed as part of the patient's standard of care at any time.

Spiral CT scans of chest, abdomen, and pelvis must be obtained; a CT of the neck must also be obtained if documented or suspected involvement in this region. A diagnostic quality CT is

required unless medically contraindicated. For patients unable to tolerate contrast-enhanced CT assessments, MRI imaging is acceptable. Patients must be evaluated with same imaging modality throughout the study for efficacy assessments. If any other radiographic or disease assessment examination is conducted per standard of care, the assessment information will be collected in the CRF.

The determination of antitumor activity will be based on objective response assessments made according to RECIST Version 1.1 (for primary and secondary endpoints) and iRECIST (for exploratory endpoints). Treatment decisions by the investigator will be based on iRECIST.

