9.2.4. Progression-Free Survival

PFS is defined as the time from start of study treatment to first documentation of objective progression of disease (PD per RECIST v1.1 or per investigator claim of clinical progression), or to death due to any cause, whichever comes first. For patients who are enrolled but fail to receive study treatment, the enrollment date will be used as the starting point in the calculation of PFS.

The same censoring rules outlined in Section 9.2.2 for DOR will be applied to PFS. Patients lacking an evaluation of tumor response after their first dose will have their event time censored at Day 1.

Analysis of PFS will also be performed based on iRECIST guidelines, with iPFS defined as the time from start of study treatment to the first documentation of objective disease progression (that is subsequently confirmed). The date of progression is the first date at which progression criteria are met (i.e., the date of unconfirmed progressive disease [iUPD]), provided that confirmed progressive disease (iCPD) is established at the next assessment. Disease progression is considered to be confirmed without the confirmation scan if patient has clinical progression or becomes clinically unstable.

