9.3.1.3. Handling of Dropouts and Missing Data

Missing data will not be imputed, with the exception of AE dates while calculating duration of events and treatment-emergent status; details will be provided in the SAP. For time-related endpoints, e.g., PFS, patients who have no specified event will be censored at the time of the last valid assessment of the endpoint(s).

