# 5.5 Handling of Dropouts and Missing Data

With the exception of the scenarios covered in this section, missing data will not be imputed.

Patients who do not have at least two (initial response and confirmation scan) post-baseline response assessments will be counted as non-responders for analysis of the primary endpoint.

AE dates will be imputed for the purpose of calculating duration of events and treatment-emergent status (see Appendix AAppendix A for imputation details and Appendix B Imputation of Partial Missing Prior Therapy Dates

When calculating time since most recent prior therapy, please following the following algorithm.

The most recent prior therapy date is defined as the latest among all the prior therapies including therapy start and end date. And if prior therapies date are partially missing, please following the following imputation rule. Prior therapy dates will be imputed if both month and year are present and only day is missing.

- For prior therapy start date, impute the first day of the month.
- For prior therapy end date, impute the last day of the month or 1 day before the first dose of study drug, whichever is earlier.

Appendix C for the treatment-emergent definition). Censoring will be described in Section 6 with each planned analysis, as applicable.

Unless otherwise specified, lab values which are recorded or provided as being less than the lower limit of quantification (LLOQ), will be included in figures and summaries as LLOQ/2. For the purpose of grading, lab values reported as less than LLOQ will be imputed as LLOQ.

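### PFS counts any death as an event, but the Day-1 censoring rule makes no exception for death or clinical progression before the first post-dose tumor evaluation

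*SAP*

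**What the plan says.** SAP section 6.6.1.4 runs PFS from the start of treatment to progression by RECIST v1.1, clinical progression or death from any cause, whichever is first. It gives the formula "PFS = Date of first documented PD or death - Date of first study treatment +1". It carries over the DOR censoring rules and then adds: "Patients lacking an evaluation of tumor response at baseline and/or after their first dose will have their event time censored at Day 1".

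Protocol section 9.2.4 has the same event definition and censors at Day 1 those patients "lacking an evaluation of tumor response after their first dose will have their event time censored at Day 1". It lacks the SAP's extra words about baseline.

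Three other provisions bear on the point:

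- SAP section 6.6.1.2, among the DOR rules applied to PFS: "Patients who have deaths or PD per RECIST v1.1 occurring after two or more missed visits will be censored at the last disease assessment".
- Protocol section 9.3.1.3, on time-related endpoints and naming PFS as the example: "patients who have no specified event will be censored at the time of the last valid assessment of the endpoint(s".
- Protocol section 7.2 schedules tumor imaging every 6 weeks from Cycle 1 Day 1, so the first post-dose scan is due at week 6.

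**The concern.** A patient who receives study drug and dies before the first scan is in the all treated set, which is the primary set for efficacy. The definition and the formula make that death an event. The Day-1 sentence makes the same patient a censored observation at the origin. No order of precedence is given, so two programmers could both follow the plan and produce different PFS curves.

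The same gap covers a patient with investigator-claimed clinical progression and no post-dose evaluation. Such cases should be rarer, because the end-of-treatment visit (protocol section 6.5) calls for a CT.

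The censoring would be informative, because the patients removed are those who failed earliest. At stake are the PFS medians and curves, which the SAP reports by expansion cohort and overall. Some cohorts are small (about 25 patients in Part B Cohort 2, about 40 in Part D).

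**Working it through.** **Text check.** Take a treated patient who dies on study Day 30 with no post-dose scan.

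- PFS definition and formula: 29 + 1 = 30 days, event.
- Day-1 sentence: 1 day, censored.
- Missed-visit rule: not triggered. The first scan is not yet due, so no visit has been missed. The rule singles out deaths after two or more missed visits, which implies that other deaths count.
- Protocol section 9.3.1.3: censoring is described for patients with no event, and this patient has one.
- For context, under SAP section 5.5 patients without the two required post-baseline assessments "will be counted as non-responders for analysis of the primary endpoint", and under SAP section 6.6.1.5 the death is an OS event. These are rules for other endpoints. They show that only PFS, read literally, drops the patient.

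**Direction.** The documents state no PFS sample size, event count or power, so there is no planned figure to reproduce. Suppose k of N patients die before any post-dose evaluation, f = k/N, and nobody else is censored in that period. Counted as events, these deaths pull the Kaplan-Meier curve down by the share f. Censored at Day 1, they leave the risk set before any event. After the last such death the estimate becomes

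S'(t) = S(t) / (1 − f),

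which exceeds S(t) whenever f > 0.

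**Illustration of size.** Inputs:

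- N = 40, the planned size of Part D.
- Exponential PFS with a median of 5.5 months. This is an assumption. The figure is the one protocol section 3.2.3.4 gives for chemotherapy in the PD-L1 CPS<10 population; it is not a planning value for this regimen.
- k = 1 or 2, also assumed.

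λ = ln 2 / 5.5 = 0.1260 per month. The shifted median is −ln[0.5(1 − f)] / λ.

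- k = 1, f = 0.025: −ln(0.4875) / 0.1260 = 5.70 months, a shift of +0.20.
- k = 2, f = 0.05: −ln(0.475) / 0.1260 = 5.91 months, a shift of +0.41.

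Six-month PFS is exp(−6λ) = 46.9% when the deaths count. Divided by 0.975 it becomes 48.2%, and divided by 0.95 it becomes 49.4%.

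**Sampling error for comparison.** With 40 events, an approximate 95% interval for a median of 5.5 is 5.5 × exp(±1.96/√40) = 4.03 to 7.50 months. Both shifts lie well inside it.

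**The case against.** The strongest reply is that the plan already puts events first. Protocol section 9.3.1.3 says who is censored (patients without an event), the DOR rules say where (the last disease assessment), and the Day-1 sentence only supplies a date when no such assessment exists. On that reading there is no conflict and no bias.

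A second reply is that literal reading proves too much. Protocol section 4.4.2 lists death among the reasons for leaving the study, and a DOR rule applied to PFS censors patients removed from the study before documented progression. Taken literally, that rule would censor every death without prior progression and empty the death component. The rules make sense only if events come first.

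Much of this stands. The event-first reading is probably what was meant, so any bias is conditional on the literal reading. The second reply also shows that a repair must deal with removal from study because of death, or that rule could censor the early death again.

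It does not remove the defect. Section 9.3.1.3 is a general protocol statement and does not say that it overrides the specific sentence, which the SAP repeats. SAP section 5.5 sends the analyst to SAP section 6 for censoring, and the unqualified sentence is what stands there.

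**Conclusion.** The point holds as an unresolved conflict between two stated rules, worth fixing before the analysis is run. If the Day-1 sentence is followed literally, early deaths disappear and the PFS estimate can only move up. If it is read as a default for event-free patients, nothing changes.

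The size rests on an early-death fraction that the documents do not give, and its lower end is zero. The shifts of 0.20 and 0.41 months for 1 and 2 of 40 are illustrations under an exponential curve with an assumed 5.5-month median.

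A reader might infer that reported PFS will be overstated. The documents do not support that: they leave the event-first reading open, and they do not show that any patient dies before a post-dose evaluation. A reader might also derive an early-death rate from the protocol's statement that patients with metastatic TNBC "have a median overall survival (OS) of less than 1 year". That describes the disease in general, and a constant hazard would probably overstate early death in patients required to have ECOG status 0 or 1.

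ORR and OS are untouched. PFS is a secondary, descriptive endpoint and SAP section 5.7 plans no formal hypothesis test, so the correction concerns an estimate and no decision rule. The SAP's extra limb on missing baseline evaluations should be nearly empty, since eligibility requires measurable disease; no direction of bias is claimed for it.

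**What to change.** In SAP section 6.6.1.4, replace the Day-1 sentence with:

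> Patients without a PFS event (PD, clinical progression or death) who lack a baseline or post-dose tumor evaluation will be censored at Day 1. A death or clinical progression before the first post-dose evaluation is a PFS event on its own date; leaving the study because of death is not removal from study under the DOR censoring rules. The existing rules for new antitumor treatment and for two or more missed visits still apply, with Day 1 as the censoring date if there is no post-dose evaluation.

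Record the change in SAP section 8, noting that it supersedes the matching sentence in protocol section 9.2.4. Protocol section 9.3 asks for an amendment only when a change in analysis methods alters site conduct, which this does not. SAP section 1 provides the route: a SAP amendment before database lock or, failing that, documentation in the study report.

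The cost is three sentences, one line in section 8 and a small programming change, with no new data. The downside is that median PFS may read slightly lower than under the literal rule.

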# 6.6.1.5 Overall Survival (OS)

OS is defined as the time from start of study treatment to date of death due to any cause. For patients who are enrolled but fail to receive study treatment, the enrollment dates will be used as the starting point in the calculation in OS. Specifically,

OS = Date of death – Date of first study treatment + 1

In the absence of confirmation of death, OS will be censored at the last date the patient is known to be alive.

Overall survival will be analyzed using Kaplan-Meier methodology and Kaplan-Meier plots will be provided. The median OS and its two-sided 95% confidence intervals (CI) will be calculated using the complementary log-log transformation method (Collett 1994).

# 6.6.2 Pharmacokinetics and Immunogenicity Endpoints

# 6.6.2.1 Pharmacokinetics and Immunogenicity Analyese

LV (ADC), total antibody, and MMAE concentrations will be listed at each PK sampling time point. Selected PK parameters for LV, total antibody, and MMAE will be estimated by noncompartmental analysis and summarized using descriptive statistics.

The ATA incidence rate is defined as the proportion of patients that develop SGN-LIV1A ATA at any time during the study.

The incidence of ATA will be summarized using the safety analysis set.

# 6.7 Safety Analyses

The safety analysis set will be used to summarize all safety endpoints.

Adverse events will be coded using Medical Dictionary for Regulatory Activities (MedDRA) Version 19.1 or higher.

Laboratory values will be graded according to the National Cancer Institute (NCI) Common Terminology Criteria for Adverse Events (CTCAE) Version 4.03 or higher.

Concomitant medications will be coded using WHO Drug (version: June 2016 or more recent).

#### 6.7.1 Adverse Events

Adverse events will be summarized by MedDRA Preferred Term in descending frequency of occurrence unless otherwise specified. For incidence reporting, if a patient reports more than one AE that was coded to the same system organ class or preferred term, the patient will be counted only once for that specific system organ class or preferred term.

A treatment-emergent AE(TEAE) is defined as a newly occurring or worsening AE after the first dose of study drug, through EOT visit or 30 days after last dose date whichever is later or through EOT visit or 90 days after last dose date for SAE. See Appendix C for details

Study SGNLVA-002 Ladiratuzumab vedotin Statistical Analysis Plan Seagen, Inc. - Confidential 01-May-2024 Page 19 of 32 regarding treatment-emergent classification. An overall summary of AEs will be provided. Summaries of AEs will be provided for the following, by preferred term, if not specified otherwise:

- All treatment-emergent AEs
- Treatment-emergent AEs related to SGN-LIV1A
- Treatment-emergent AEs related to both SGN-LIV1A and Pembro
- Treatment-emergent Serious Adverse Events (SAEs)
- Treatment-emergent SAEs related to SGN-LIV1A
- Treatment-emergent SAEs related to both SGN-LIV1A and Pembro
- Treatment-emergent AEs leading to dose delay of SGN-LIV1A
- Treatment-emergent AEs leading to dose reduction of SGN-LIV1A
- Treatment-emergent AEs leading to treatment discontinuation
- Treatment-emergent AEs leading to death
- Infusion-related reactions by preferred term
- DLTs
- Treatment-emergent AEs by system organ class, preferred term and maximum severity.
- Grade 3–5 treatment-emergent AEs
- Treatment-emergent AEs by system organ class and preferred term

All adverse events, adverse events leading to treatment discontinuation, and adverse events leading to death will be listed.

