3.1.5.1. Dose-Limiting Toxicity in Part A

A DLT in Part A is defined as 1 of the following that is considered related to LV or the combination, and cannot be attributed to pembrolizumab alone:

- Any clinically significant, non-hematologic AE ≥ Grade 3 according to the National Cancer Institute Common Terminology Criteria for Adverse Events (NCI CTCAE), Version 4.03 (exceptions noted in list below)
- ≥ Grade 3 febrile neutropenia
- Grade 4 thrombocytopenia or Grade 3 thrombocytopenia associated with clinically significant bleeding that requires medical intervention
- Grade 4 anemia unrelated to underlying disease
- Discontinuation during Cycle 1 due to treatment-related toxicity
- Prolonged delay (>2 weeks) in initiating Cycle 2 due to treatment-related toxicity
- Grade 5 event (death)

The following events will not be considered a DLT:

- Grade 3 fatigue that improves to ≤ Grade 1 within 3 days with or without medical assessment
- Grade 3 tumor pain that improves to ≤ Grade 1 within 3 days with or without medical assessment

- LV infusion: Grade 3 infusion-related reactions (IRRs) that resolve within 1 day with or without medical assessment
- ≥ Grade 3 non-hematological laboratory abnormalities that resolve to ≤ Grade 1 within 7 days with or without optimal medical management
- Isolated Grade 3 or 4 electrolyte imbalances/abnormalities and Grade 3 elevations in blood glucose not associated with clinical sequelae that are corrected with supplementation/appropriate management within 3 days
- Grade 3 rash that improves to ≤ Grade 2 within 3 days with or without medical assessment
- Grade 3 nausea that improves to ≤ Grade 1 within 3 days with or without medical assessment
- Grade 3 diarrhea that improves to ≤ Grade 1 within 3 days with or without medical assessment
- Grade 3 vomiting that improves to ≤ Grade 1 within 3 days with or without medical assessment

The following event will not be considered DLT evaluable:

 Pembrolizumab infusion: ≥ Grade 3 IRRs – these patients must be discontinued from pembrolizumab (see Sections 5.3.5, 9.3.1.7), and are not evaluable for DLTs.

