Hospitalization:	The AE resulted in hospitalization or prolonged an existing inpatient hospitalization. Hospitalizations for elective medical or surgical procedures or treatments planned before the signing of informed consent in the study or routine check-ups are not SAEs by this criterion. Admission to a palliative unit or hospice care facility is not considered to be a hospitalization. Hospitalizations or prolonged hospitalizations for scheduled therapy of the underlying cancer or study target disease need not be captured as SAEs.
Disabling/ incapacitating:	An AE that resulted in a persistent or significant incapacity or substantial disruption of the patient's ability to conduct normal life functions.
Congenital anomaly or birth defect:	An adverse outcome in a child or fetus of a patient exposed to the molecule or study treatment regimen before conception or during pregnancy.
Medically significant:	The AE did not meet any of the above criteria but could have jeopardized the patient and might have required medical or surgical intervention to prevent one of the outcomes listed above or involves suspected transmission via a medicinal product of an infectious agent. Potential drug-induced liver injury (DILI) also is considered a medically significant event. (see Section 7.5.1.2 for the definition of potential DILI.)

Adverse Event Severity

AE severity should be graded using the NCI CTCAE, version 4.03. These criteria are provided in the study manual.

AE severity and seriousness are assessed independently. 'Severity' characterizes the intensity of an AE. 'Serious' is a regulatory definition and serves as a guide to the sponsor for defining regulatory reporting obligations (see definition for SAEs, above).

Relationship of the Adverse Event to Study Treatment

The relationship of each AE to each study treatment (LV, pembrolizumab) should be evaluated by the investigator using the following criteria:

Amendment 11: 19-Oct-2023

Page 76 of 152

Related:

There is evidence to suggest a causal relationship between the drug and the AE, such as:

A single occurrence of an event that is uncommon and known to be strongly associated with drug exposure (e.g., angioedema, hepatic injury, Stevens-Johnson Syndrome)

One or more occurrences of an event that is not commonly associated with drug exposure, but is otherwise uncommon in the population exposed to the drug (e.g., tendon rupture)

Unrelated:

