9.3.9.2. Adverse Events

An overview of AEs will provide a tabulation of the incidence of all AEs, treatment-emergent AEs, treatment-related AEs, Grade 3 and higher AEs, SAEs, treatment-related SAEs, deaths, and AEs leading to study treatment discontinuation. AEs will be defined as treatment emergent if they are newly occurring or worsen following study treatment.

AEs will be listed and summarized by Medical Dictionary for Regulatory Activities (MedDRA), preferred term, severity, and relationship to study drug. In the event of multiple occurrences of the same AE with the same preferred term in 1 patient, the AE will be counted once as the occurrence. The incidence of AEs will be tabulated by preferred term and treatment group. AEs leading to premature discontinuation of study drug will be summarized and listed in the same manner.

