#### 2 OBJECTIVES AND ENDPOINTS

Primary Safety Objectives	Corresponding Endpoint

 
Assess the safety and tolerability of the combination of SGN-LIV1A and pembrolizumab in patients with LA/M TNBC
 
Identify the recommended dose of SGN-LIV1A in combination with pembrolizumab in patients with LA/M TNBC
 
	Type, incidence, severity, seriousness, and relatedness of AEs     Laboratory abnormalities     Incidence of dose-limiting toxicity (DLT)
Primary Efficacy Objective	Corresponding Endpoint
Evaluate the confirmed ORR of the combination of SGN-LIV1A and pembrolizumab in patients with LA/M TNBC	Confirmed ORR as determined by the investigator according to RECIST v1.1
Secondary Efficacy Objectives	Corresponding Endpoints
Evaluate the DOR, DCR, PFS, and OS	DOR as determined by RECIST v1.1     DCR as determined by RECIST v1.1     PFS as determined by RECIST v1.1     OS
Exploratory Efficacy Objectives	Corresponding Endpoints

Evaluate the ORR, DOR, DCR, and PFS according to iRECIST	ORR as determined by iRECIST  DOR as determined by iRECIST  DOR as determined by iRECIST  PFS as determined by iRECIST
Pharmacokinetic and Immunogenicity Objectives	Corresponding Endpoints
Assess PK and incidence of antitherapeutic antibodies (ATAs) of SGN-LIV1A	Selected PK parameters for SGN-LIV1A, and MMAE     Incidence of ATAs to SGN-LIV1A
Biomarkers Objectives	Corresponding Endpoints
Evaluate PD-L1 and LIV-1 expression-response relationship     Assess exploratory biomarkers (e.g., in the tumor immune microenvironment or periphery) of study treatmentmediated pharmacodynamic effects	PD-L1 and LIV-1 expression-response relationship following treatment with SGN- LIV1A and pembrolizumab     Relationship between biomarkers in blood and tumor tissue to efficacy, safety, or other biomarker endpoints following treatment with SGN-LIV1A/pembrolizumab

RECIST = Response Evaluation Criteria in Solid Tumors; iRECIST = immune-related RECIST.

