# 6.7.1.1 Adverse Events of Special Importance(AESI)

Adverse events of peripheral neuropathy may be considered AEs of special importance. Other AEs such as neutropenia may be added to AEs of special importance, as necessary. The definition of adverse events of special importance and search criteria will be maintained in a separate document and will be finalized prior to database lock. AESI will be summarized by MedDRA Preferred Term in descending frequency of occurrence.

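### SAP 6.7.1 plans by-term relatedness tables for LV and for both drugs but none for pembrolizumab, so pembrolizumab-only events and the any-pembrolizumab total are not reported by term

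*SAP*

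**What the plan says.** Section 2 of the SAP makes "Type, incidence, severity, seriousness, and relatedness of AEs" a primary safety endpoint. Protocol 7.5.1.1 sets how relatedness is collected: "The relationship of each AE to each study treatment (LV, pembrolizumab) should be evaluated by the investigator". Protocol 9.3.9.2 then plans the reporting: "AEs will be listed and summarized by Medical Dictionary for Regulatory Activities (MedDRA), preferred term, severity, and relationship to study drug". The same section describes an AE overview that includes treatment-related AEs and treatment-related SAEs, without a split by drug.

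SAP 6.7.1 turns this into a list of 15 summaries. The relatedness entries are AEs and SAEs related to LV, plus "Treatment-emergent AEs related to both SGN-LIV1A and Pembro" and "Treatment-emergent SAEs related to both SGN-LIV1A and Pembro". The SAP also promises an overall AE summary, but does not state its contents. All AEs will be listed.

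SAP 8.2 gives eight changes, mainly attributed to the move from a full to an abbreviated study report. None concerns relatedness. SAP 8.1, on changes from the protocol, only refers to 8.2.

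**The concern.** The trial tests a two-drug combination, and its first primary objective is the safety and tolerability of that combination. The data record causality for each drug, but the tables carry it through for LV and for the overlap only. Nothing planned shows, by preferred term, which events investigators attributed to pembrolizumab.

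Pembrolizumab-only events are foreseeable. Patients who stop LV may stay on pembrolizumab (Protocol 4.4.1 and 5.3.5.3). Immune-related events may appear months after the last pembrolizumab dose (Protocol 5.3.5.1), and SAEs are collected to at least 90 days after treatment (Protocol 7.5.1.3). Protocol 3.2.2 expects hepatic and gastrointestinal toxicities of the two drugs to overlap, and Protocol 5.6.2 ties the pembrolizumab management guidance to the investigator's attribution. The report would omit, by term and dose level, the attribution on which that guidance depends.

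The dose-limiting toxicity table does not recover these events. In Parts A and C such a toxicity must be "considered related to LV or the combination, and cannot be attributed to pembrolizumab alone".

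**Working it through.** The plan states no figure to reproduce. The check is to follow each possible attribution through the planned outputs.

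**Count of summaries in SAP 6.7.1.** There are 15 in total. By relatedness there are 4: two for LV (AEs, SAEs) and two for both drugs (AEs, SAEs). The other 15 − 4 = 11 are not by relatedness. None of the 15 is for pembrolizumab as such.

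**Where an event goes, by the investigator's attribution.**

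| Attribution | All-AE tables and listing | LV tables | Both-drug tables | Treatment-related lines of the overview |
|---|---|---|---|---|
| LV only | yes | yes | no | yes |
| Both drugs | yes | yes, if the title means any LV attribution | yes | yes |
| Pembrolizumab only | yes | no | no | yes, not split by drug |
| Neither | yes | no | no | no |

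The last column assumes that the SAP's overall summary follows Protocol 9.3.9.2 and counts attribution to either drug as treatment-related.

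**Can the missing counts be derived?** Take one preferred term at one dose level, with at most one event of that term per patient. Let T be the patients with the term, L those in the LV table, B those in the both-drug table, P those with a pembrolizumab-only event and U those with an unrelated event.

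- If the LV table means any LV attribution, T = L + P + U. The tables give only P + U = T − L. So P can be anywhere from 0 to T − L, and the any-pembrolizumab count, B + P, anywhere from B to B + T − L.
- If the LV table means LV only, T = L + B + P + U. Then P runs from 0 to T − L − B, and the any-pembrolizumab count from B to T − L.

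On either reading, pembrolizumab-only and unrelated events are pooled in one remainder and cannot be separated. The same algebra holds for SAEs.

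**What the overview adds.** Let R be the patients with any treatment-related AE, and suppose that the LV table has an any-event row on the any-LV reading. Then R minus that row is the number of patients whose related AEs were all pembrolizumab-only. This is a lower bound on patients with a pembrolizumab-only event, because a patient who also had an LV-related event is subtracted out. It identifies no term and does not give the any-pembrolizumab total.

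**The case against.** The strongest case on the other side has four parts.

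- **The both-drug tables already show pembrolizumab relatedness.** This is correct. Every event in them is pembrolizumab-related, so a reader would be wrong to infer that no planned table shows pembrolizumab attribution. What is missing is the pembrolizumab-only events and the any-pembrolizumab total.
- **The overview covers the rest.** It does so in part. A pembrolizumab-only event would naturally count there as treatment-related, but by neither drug nor term.
- **The report is deliberately abbreviated, and the protocol speaks of study drug without naming pembrolizumab.** Both statements are true. However, SAP 8.2 lists what changed and relatedness is not there, while Protocol 7.5.1.1 makes causality a per-drug assessment.
- **The consequence is slight.** The data are listed, no formal hypothesis testing is planned (SAP 5.7), and attribution is a judgment. This stands as a limit on importance. The subjectivity applies equally to the LV and both-drug tables already planned.

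A reader might also infer that grouped counts of immune-related events are ruled out, because SAP 6.7.1.1 says "AESI will be summarized by MedDRA Preferred Term in descending frequency of occurrence". The documents do not support this. The definition and search criteria for AEs of special importance are in a separate document not available here, and the sentence does not exclude group or any-event rows. The documents contain no term list to show which Protocol Table 7 categories span several preferred terms. SAP 6.7.1 does plan "Treatment-emergent AEs by system organ class, preferred term and maximum severity", and SAP 6.7.5 summarizes liver safety. Grouped tables of immune-related events are an optional reporting preference, and this point does not ask for them.

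**Conclusion.** The point holds as a minor reporting gap with an inexpensive remedy. Two tables are missing from SAP 6.7.1: pembrolizumab-related treatment-emergent AEs, and the same for SAEs. Without them, reporting of a primary safety endpoint is incomplete for one of the two study drugs.

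No numerical effect is claimed. The events do not disappear from the report, since they are in the all-AE tables and the listing. The documents give no basis for inferring an effect on sample size, efficacy estimates, dose-limiting toxicity decisions or safety monitoring.

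The conclusion rests on reading the SAP 6.7.1 list as the set of planned tables, and on the overall AE summary having no more relatedness detail than Protocol 9.3.9.2 describes. If that summary were already split by drug, any-event totals for pembrolizumab would be available. The by-term gap would remain.

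**What to change.** In SAP 6.7.1, add two summaries by preferred term: treatment-emergent AEs related to pembrolizumab, and treatment-emergent SAEs related to pembrolizumab. In each, show any pembrolizumab attribution and pembrolizumab only as separate columns, by dose level and overall, with each patient counted once per term. State in the titles of the existing LV tables whether they mean any LV attribution or LV only.

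The SAP allows amendment before database lock. After lock, the tables can still be produced and documented in the study report, where SAP 5.1 would class them as exploratory. With no hypothesis tests planned, that label costs little.

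The cost is a few extra tables from causality data already collected for each drug, with no change at sites. One limit should be stated beside them: with no pembrolizumab-alone arm, attribution rests on investigator judgment, so the tables describe events under the combination and do not isolate the effect of pembrolizumab.
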